12.1. Selection criteria

Inclusion

Human peripheral blood obtained from adult donors with the following characteristics:

- Patients with $\text{BMI} \geq 30\text{kg/m}^2$
- With risk factors for type 2 diabetes (history of diabetic parents or siblings, sedentary habits)
- Fasting blood glucose $\leq 126 \text{ mg/dL}$ or glycosylated hemoglobin $< 6.5\%$
- Controlled arterial hypertension
- >18 years of age
- Accept and sign the informed consent

No inclusion

- Hypersensitivity to the components of the formula
- History of hypoglycemic episodes
- History of obesity of endogenous origin
- History of serious psychological, psychiatric, eating or neurological disorders

- History of hyperthyroidism, heart disease, diabetes, liver or kidney failure, glaucoma, epilepsy
- Pregnancy or lactation

Exclusion criteria

- Pregnancy
- Diabetics
- Presenting any serious adverse effect
- Patients who decide to withdraw from the protocol

Elimination

- Samples contaminated during processing
- Lysed blood samples
- Coagulated blood simple.

Variable Description

Independent Variable

Berberine

Category: quantitative.

Measurement scale: ratio.

Measurement unit: 500 mg with excipient q.s.

Operational definition: the tested dose of Berberine was 500 mg, given to patients for 3 months.

Dependent

Gene expression of IL-1 β , TNF- α and NLRP3.

Category: quantitative.

Measurement scale: discrete, continuous.

Measurement unit: arbitrary units.

Operational definition: Cytokines were determined with commercial qPCR equipment/reagents, and their arbitrary units/relative expression were determined by a specific standard curve for each one.

Observation method: open.

Sampling method: non-probabilistic sampling of consecutive comparative groups that met the selection criteria, until reaching the sample size that constituted the study groups (patients with exogenous obesity).

Operational description of the study: Berberine has been provided by the Medix laboratory, in 500 mg capsules, to treat patients for 3 months.

Study groups

The individuals will be distributed into four groups:

- Group 1. Individuals with exogenous obesity: nutritional plan intervention for lifestyle change.
- Group 2. Individuals with exogenous obesity: nutritional plan intervention, moderate controlled aerobic exercise for lifestyle change.

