- Group 3. Individuals with exogenous obesity: nutritional plan intervention, moderate aerobic exercise and Berberine phytopharmaceutical. With biweekly sessions for 3 months.
- Group 4. Normal-weight individuals without intervention.

Blood samples were taken after informed consent from the participants, they were informed of the intervention and the group to which they belonged, they were also taken at the end of the study.

Procedure

In the selection, obtaining information, anthropometry and blood biochemistry, the subjects of the study will be asked for authorization and their participation will be requested after a detailed explanation of the risks and benefits of the protocol, obtaining signed informed consent.

Obtaining the samples

The universe of the study will be individuals from 19 to 55 years of age with exogenous obesity; they will be recruited in the Obesity Projects area of the Postgraduate Studies and Research section of the Higher School of Medicine of the National Polytechnic Institute, referred by the Comprehensive Medical Service.

Each participant will be asked in writing to enter the study, each one was identified, and a clinical history was prepared with anthropometric measurements: weight, percentage of body fat, percentage of visceral fat, height, BMI. Peripheral blood will also be taken for blood biochemistry and messenger RNA extraction and qPCR tests to determine gene expression of NLRP3, IL-1 β and TNF- α .

Biochemical tests.

Peripheral blood samples will be evaluated by an external laboratory.

Blood samples will be collected at the beginning and three months after treatment. Participants were called at 7 am, after fasting for at least 8 hours, and the sample was collected in Vacutainer tubes (BD, USA), added with ethylenediaminetetraacetic acid (EDTA) to prevent coagulation. 4 mL of blood was taken from everyone; from there, 1 mL of Trizol (Sigma-Aldrich, USA) was added to 2 2 mL tubes with 100 μ L per tube. The blood was vortexed for 30 s and stored at -70 °C until processing. The rest of the blood was stored at -20 °C.

Anthropometric evaluation

The somatometry of each participant will be determined by wearing light clothing and without shoes: weight, height, % body fat, % visceral fat.

Height

It will be defined as the distance between the vertex and the support plane.

- Instrument: Stadiometer (Seca mod. 208).
- The measurement will be expressed in cm with a precision of 1 mm.

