“Low-calorie” Mediterranean diet: This is the model supported by SEEDO because it represents this balanced and healthy approach, with a low intake of saturated and trans fatty acids and added sugars, and a high consumption of vegetable fiber and monounsaturated fatty acids. Its health benefits, including mortality, are clearly established in the literature.

High-protein diet: Based on the satiating effect and less loss of lean mass. The intake is increased to >1.2 g/kg/day, with a minimum intake of 90 g daily.

Nutritional Management

The nutritional management plan in this project will be aimed at improving the lifestyle and quality of life of patients, as well as reducing their body weight. This intervention will be done according to the nutritional management for obesity developed by nutritionists from INCMNSZ.

The goals of the nutritional plan were to establish healthy eating habits with a 10-15% reduction in body weight during treatment.

Nutritional Consultations

The consultations will be biweekly to evaluate body weight, anthropometry and adherence to the nutritional regimen, in addition to monitoring the modification of eating habits.

Clinical-nutritional history

In this clinical history, the lifestyle of the patients will be evaluated, the activities from the time they will wake up until bedtime will be questioned, their physical activities, allergies or intolerances, eating habits such as: meal times, tastes, preferences, quantities, type of food preparation, economic amount allocated, places of food, if they ate with electronic distractions, among others, to know the needs of each participant and adequately prescribe the food plan.

Food frequency

A food frequency survey from ENSANUT 2012 will be applied to learn about eating habits and determine the consumption of energy, important macro and micronutrients. The same survey analyzes and reports the results when capturing the data. With the evaluation of the diet and the anthropometric, biochemical, clinical, dietary and economic indicators, a nutritional diagnosis and the degree of obesity of each patient were established.

Energy expenditure

After the diagnosis, the prescription of the individualized food plan was prepared. The basal energy expenditure (BEE) was calculated with the Harris Benedict formula, and the current body weight.

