A bottle of Berberine of 500 mg with excipient cbp of 102 tablets each was given, as well as a new bottle at each consultation and the participants handed over the empty bottles or with leftover pills. The way they should ingest them was 3 tablets: 3 times a day before each meal.

Treatment adherence log

The patients will give a treatment adherence log to indicate the day and time they took the tablets, as well as if they did not take them.

Adverse effects log

The patients will give a log in which they should indicate if they had any adverse events, to report them.

Controlled Aerobic Exercise

Controlled aerobic exercise on a treadmill, supervised by a sports physician, the frequency with which participants carried out their sessions was 3 times a week for 30 minutes each, at 60-70% of maximum heart rate. Due to the sedentary lifestyle of the patients, coupled

with obesity and its complications, an 'app' was installed on the participants' cell phones (with the exception of two: one did not have the device and one could not read or write, so they were provided with a semi-automated pedometer so that all participants had the same intervention), all were asked if they exercised, which was denied and their usual physical activity was minimal; in the initial phase of the protocol, their usual physical activity was determined (using the 'app'), which they were instructed to increase, with a goal of 10,000 steps or 150 min per week.

Gene expression

Extraction of total RNA

Blood samples will be lysed, and the material was extracted with TRIzol®Reagent, a mixture of guanidine isocyanate and phenol-chloroform, following the manufacturer's instructions. Once isolated, the total RNA will be suspended in RNase-free water to prevent its degradation and stored at -80°C. 140 µL of peripheral blood were used.

Extraction technique

Sample lysis will be carried out by adding one milliliter of TRIzol reagent and allowing it to incubate for 10 minutes.

1) Separation phase. Phenol-chloroform (0.2 mL per sample) was added, and the mixture was then centrifuged. Three phases were separated: a lower organic phase with the proteins, an interface with the DNA, and a transparent upper aqueous phase with the RNA. This fraction was transferred to a new tube to precipitate the RNA.

2) RNA precipitation by adding 0.5 mL of isopropyl alcohol. Centrifugation at 12,000g for 10 min at 4°C occurs, and the precipitated RNA forms a pellet or adheres to the walls and base of the tube.

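### Harms are collected only through a participant-written log, with no stated groups, staff question, review or summary, so events can be missed and may not be comparable between groups

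*Combined protocol and SAP*

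**What the plan says.** All references are to the combined protocol and SAP, Material and methods.

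- **Adverse effects log:** "The patients will give a log in which they should indicate if they had any adverse events, to report them". No group is named.
- **Treatment adherence log**, immediately before it: "The patients will give a treatment adherence log to indicate the day and time they took the tablets". Tablets go to one group only under Study groups: "Group 3. Individuals with exogenous obesity: nutritional plan intervention, moderate aerobic exercise and Berberine phytopharmaceutical". Group 2 has the nutritional plan and the exercise without berberine.
- **Nutritional Consultations**, on what each visit covers: "The consultations will be biweekly to evaluate body weight, anthropometry and adherence to the nutritional regimen", together with changes in eating behaviour. No question about harm is listed.
- **Phytopharmaceutical:** a new bottle is issued at each consultation, and empty bottles or leftover tablets are returned. Nothing is said about collecting or reading the adverse effects log.
- **Controlled Aerobic Exercise:** two participants could not use the phone application, because "one did not have the device and one could not read or write". The remedy covers step counting only: "so they were provided with a semi-automated pedometer so that all participants had the same intervention".
- **Exclusion criteria:** "Presenting any serious adverse effect" is listed, without a definition or a route by which such an effect would come to light.
- **Statistical analysis:** no summary or comparison of adverse events is planned.

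**The concern.** A log that participants fill in themselves records what they notice, think worth writing and are able to write. The plan has a regular staff contact at which a harm question could be asked, but does not use it for that. The exclusion criterion for serious adverse effects has no described source of information other than this log.

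The second issue is comparability. Group 3 receives berberine on top of a calorie deficit and treadmill exercise, and any of the three could cause symptoms. Group 2 has the same diet and exercise, so it is the natural reference for harms. That reference works only if Groups 2 and 3 are observed in the same way. The log's place beside the tablet log leaves it open whether Group 2 is observed at all. If it is not, a symptom recorded in Group 3 cannot be attributed to berberine rather than to the diet or the exercise.

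**Working it through.** The plan gives no adverse event rate, harm analysis or sample size calculation, so there is no figure to reproduce. The main check is textual, and the arithmetic only shows scale.

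**1. Possible routes by which a harm could be recorded**

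| Place | Contact or record | Described as harm collection? |
|---|---|---|
| Adverse effects log | Participant writes | Yes; group and reviewer not stated |
| Nutritional Consultations | Staff, every two weeks | No |
| Bottle exchange | At each consultation | No |
| Controlled Aerobic Exercise | Sports physician, 3 times a week | No |
| Biochemical tests | Start and three months | No |
| Statistical analysis | ANOVA and t tests | No adverse event output |

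One route is described, and it is passive.

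**2. Events missed by incomplete capture**

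Inputs: 90 obese patients in three groups (Study subjects, Study groups). An equal split, 90/3 = 30 per group, is an assumption. The true harm rate p and the captured fraction c are also assumptions.

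Chance that at least one case is recorded = 1 − (1 − p·c)^30.

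| True rate p | c = 1 | c = 0.75 | c = 0.5 | c = 0.25 |
|---|---|---|---|---|
| 5% | 78.5% | 68.2% | 53.2% | 31.4% |
| 10% | 95.8% | 90.4% | 78.5% | 53.2% |

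For example, with p = 5% and c = 0.5: 1 − 0.975^30 = 53.2%.

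An empty log is also hard to read. With 0 of 30 recorded, the one-sided 95% upper bound is 1 − 0.05^(1/30) = 9.5%, but only if capture is complete. At half capture the same zero is compatible with 9.5%/0.5 = 19.0%.

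**3. Apparent difference from unequal capture**

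Let the true rate r be the same in Groups 2 and 3, with full capture in Group 3 and a fraction c in Group 2. Apparent excess on berberine = r − r·c = r(1 − c).

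| True rate r | c = 0 | 0.25 | 0.5 | 0.75 | 1 |
|---|---|---|---|---|---|
| 10% | 10 | 7.5 | 5 | 2.5 | 0 |
| 20% | 20 | 15 | 10 | 5 | 0 |
| 30% | 30 | 22.5 | 15 | 7.5 | 0 |

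Entries are percentage points; the true excess is 0 throughout. None of these rates comes from the documents.

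**4. What equal capture would still not give**

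Normal-approximation power, two-sided 0.05, n = 30 per group: Φ{[|d| − 1.96·√(2p̄(1−p̄)/n)] / √(p₁(1−p₁)/n + p₂(1−p₂)/n)}.

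- 5% v 20%: (0.15 − 1.96 × 0.0854)/0.0832 = −0.21, power about 42%.
- 10% v 30%: (0.20 − 1.96 × 0.1033)/0.1000 = −0.02, power about 49%.

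Equal capture therefore supports a description by group, not a definitive safety test.

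**The case against.** The strongest reply is that the text is silent rather than wrong. The log sentence speaks of patients in general and has its own heading. Unlike the adherence log just before it, it does not mention tablets. The criterion on serious adverse effects is not limited to one group. A sports physician supervises the exercise three times a week, and exercise belongs to Groups 2 and 3, so berberine patients and their natural comparators both meet a clinician often. Staff may well have asked about symptoms at consultations. Safety is not among the stated objectives.

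Much of this stands, and it rules out three stronger readings that a reader might infer.

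- *The log belongs to Group 3 only, so 60 of the 90 obese patients have no harm record.* This rests on where the paragraph sits. No sentence restricts the log to one group.
- *A participant was unable to complete the log.* The plan reports one person who could not read or write and does not give the group. If only Group 3 kept the log, that person may never have been given one.
- *The plan fails to test its own statement that alternatives with fewer adverse effects are needed.* That statement, in the Treatment section, concerns marketed obesity drugs. No group receives them, so a comparison of Group 3 with Group 2 would not address it.

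The reply does not remove the core. On either reading of who keeps the log, capture is passive, no reviewer or time of review is given, nothing replaces writing for someone who cannot write, and no summary by group is planned. Supervised exercise may reveal events incidentally, but it is not described as a way of recording them and is not part of Group 1's intervention.

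**Conclusion.** The point holds as a weakness in how harms are collected and reported, with a cheap remedy. The described method is a self-written log with no stated groups, staff question, review, alternative to writing or planned summary. It can miss events: under the assumptions above, half capture lowers the chance of seeing any case of a 5% harm among 30 patients from 78.5% to 53.2%.

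The loss of comparability is conditional. It arises if Groups 2 and 3 are observed differently, which the text neither states nor excludes. At an assumed common rate of 20%, the artefact runs from 20 points to 0, according to capture in Group 2. The 30 per group, the event rates and the capture fractions are all assumptions, and a misleading excess would appear only if someone compared the groups, which the plan does not propose.

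**What to change.** State that Groups 1, 2 and 3 complete the same adverse effects log. At each existing biweekly consultation, in all three groups, staff ask one fixed question about harm, write down the answer themselves (an oral report is enough), and review the log. Add to Statistical analysis a table of adverse events by group, with Group 3 versus Group 2 as the descriptive harm comparison.

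The cost is a few minutes per visit, one form used in every obese group, and more trivial events recorded. Two limits remain: the study is open, so reporting may still differ between groups, and about 30 per group (assumed) allows description only.

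The Abstract describes the patients as already studied. If collection is complete, report which groups kept the log and how it was reviewed. If capture differed between groups, make no comparative safety claim.

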Berberine has activity against bacteria, viruses, fungi, protozoa, helminths and chlamydia, with in vitro and clinical phase results. Berberine is antidiarrheal by inhibiting peristalsis and, probably, by its intestinal antisecretory action. Different clinical studies show that Berberine is effective in treating acute diarrhea caused by enterotoxins from *E. coli*, *Vibrio cholerae*, among others. It is also more effective than ranitidine for duodenal ulcers. In the cardiovascular system it has positive inotropic, negative chronotropic, anti-arrhythmic and vasodilatory action. The decrease in platelet aggregation and thromboxane B2 could be involved in its anti-ischemic effect; it also has cytostatic activity in vivo and in vitro, stimulates the secretion of bile and bilirubin, improves the symptoms of chronic cholecystitis and normalizes tyramine concentration in patients with liver cirrhosis^{110, 117, 118}.

It also has anti-tumor effects in many types of cancer, since it suppresses proliferation by inducing apoptosis, inhibiting metastasis, and has very low or no toxicity in healthy tissue and is protective in the liver against chemically induced hepatotoxicity^{111,112,113,117,118,119}.

Berberine and its interaction with obesity and inflammation

The main component of *Rhizoma coptidis* is Berberine, it is biologically active and is an over-the-counterdrug with multiple properties, among which anti-inflammation stands out, reducing IL-1 β , TNF- α , iNOS, ICAM-1, IL-6 and the activation of NF- κ B in vivo. Berberine reduces inflammation via TLR4, since it inhibits the activation of SRC and cell mobility by TLR in macrophages stimulated with LPS; in addition, it inhibits the expression of TNF- α , IL-6, TLR 2, TLR 4 and TLR 9 in early-phase sepsis in an animal model^{114,120}.

The suppression of inflammation by Berberine is a complex phenomenon, the NF- κ B pathway plays an important role, since TLR-NF- κ B mediate inflammation and could be targeted by Berberine to induce anti-inflammatory activity. Inflammatory stimuli include

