
3) RNA washing. This is done with 1 mL of 75% alcohol and centrifugation at 7500g for 5 minutes. The pellet is dried by vacuum centrifugation (spin vac pump) until the alcohol evaporates.

4) Re-suspension of total RNA. The samples are dissolved in RNase-free water, treated with 0.1% diethylpyrocarbonate (DEPC) (nuclease inhibitor). The integrity of the tRNA is checked on an agarose gel. Quantification of total extracted RNA

Sample concentration and purity will be measured by spectrophotometry (NanoDrop2000™, Thermo Fisher Scientific Inc., Waltham, Massachusetts, USA). Samples with a purity index (at 260/280nm) of 1.80-2.0 were considered adequate, indicating the absence of contamination.

Complementary DNA synthesis by reverse transcription

cDNA amplification will be performed using the “Transcriptor First Strand cDNA” kit for Rt-PCR from Roche (Roche Diagnostics GmbH, Mannheim, Germany), according to the manufacturer’s instructions. 500 µg of the cDNA sample was used in 20 µl volume. For the reaction, the following was done: The cDNA was synthesized from the tRNA of the samples and with the Invitrogen Roche kit (CA USA), in the following reaction mixture:

- 1) H₂O mili Q - 12.5 µL (the volume varies)
- 2) Buffer 10x MMLV – 2.5 µL
- 3) ‘Random primer’ - 0.5 µL
- 4) DTT 0.1 M—2.5 µL
- 5) dNTPs mix –1 µL
- 6) MMLV RT

The volume of the mixture is adjusted to 25 µL and the final product after the reaction in the conventional thermocycler (MasterCycler, Eppendorf) for 1 hour and stored at -20°C.

Real-time polymerase chain reaction, qRT-PCR

Procedure to determine the relative mRNA expression of genes of interest, using probes from the human transcriptome library (Roche, Library), LightCycler nano thermal cycler and TaqMan reaction mix (Roche Diagnostics). Oligosequences (sense and antisense) were

designed with ProbeFinder software version 2.45 (<http://www.universalprobelibrary.com>). The reaction mix was prepared according to the manufacturer's protocol with 5 μ l of cDNA of the appropriate dilution, in 10 μ l. The assay included a standard curve of 5 serial dilutions for each gene, and samples were normalized with the endogenous control β -actin. Each sample was performed in triplicate and data were analyzed with LightCycler nano software.

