The thermocycler was programmed with the following scheme: preincubation for one cycle of 10 minutes at 95°C; the reaction for 45 consecutive cycles (denaturation at 95°C for 10 seconds, annealing at 60°C for 30 seconds and extension at 72°C for 1 second) and the final incubation at 40°C for 30 seconds.

Table 5. Oligonucleotide sequences used to determine gene expression.

Gen	Proteins	Sequences	Concentration
NLRP3	Proteína 3 que contiene dominios NACHT, LRR y PY	F: 5' GCA AGA CTT TGA CAA CAT GC3' R: 3'CAC CTG TTG TGC AAT CTG AAG5'	10nM
TNF- α	Factor de necrosis tumoral alfa	F: 5' CAGCCTCTCTCCCTTGAT3' R: 3'GCCAGAGGGCTGATTAGAGA5'	10nM
IL-1 β	Interleucina 1 beta	F: 5' TTG GGT AAT TTT TGG GAT CTT AC3' R: 3'CTG TCC TGC GTG TTG AAA GA5'	10nM
B-actina	Gen constitutivo	F: 5' AGC CAC ATC GCT CAG ACA C3' R: 3'GCC CAA TAC GAC CAA ATC C5'	10nM

Statistical analysis

The values of each determination are expressed as the mean \pm SE. The differences between the groups were calculated with ANOVA. Differences between the groups will be determined by using Student's T test. In all tests, a value less than or equal to 0.05 was considered significant.

Ethical aspects

The study will be of lower than minimum risk, since no blood was obtained from the participants in quantities greater than the limit established by the Regulations for Research on Human Beings of the General Health Law. The project was evaluated,

approved and accepted by the Research and Ethics Committee of the Higher School of Medicine of the National Polytechnic Institute.

The study was carried out in accordance with the ethical principles:

- Declaration of Helsinki of the WMA - Ethical principles for medical research involving human beings¹²⁶.
- Written and signed informed consent as stipulated in article 21 of the General Health Regulations on Health Research¹²⁷.
- As stipulated in article 17 of the General Health Regulations on Health Research, this project is classified as minimal risk¹²⁷.
- The protocol was carried out in compliance with the recommendations established in NOM-087-ECOL-SSA1-2002, which addresses matters related to Environmental Protection and Environmental Health; Biological-infectious Hazardous Waste¹²⁸.

Material Resources

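### All three gene readouts are divided by one reference gene, β-actin, whose stability across groups and visits is never checked, so a fall in all three is not independent support for inhibition

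*Combined protocol and SAP*

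**What the plan says.** The general objective (section 9) and the hypothesis (section 10) concern expression of three genes, and the hypothesis is that berberine lowers all of them. The Variable Description makes these three expression levels the dependent variables, in arbitrary units of relative expression.

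Under the heading on real-time PCR, "samples were normalized with the endogenous control" β-actin. Table 5 lists it as "Gen constitutivo", that is, a constitutive gene, and lists no other reference. The same section adds "The assay included a standard curve of 5 serial dilutions for each gene" and "Each sample was performed in triplicate". RNA concentration and purity are measured by spectrophotometry, and integrity is checked on a gel. The Statistical analysis section gives ANOVA and Student's t test at 0.05. It says nothing about the reference gene.

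On amounts, the section on complementary DNA synthesis says 500 µg "of the cDNA sample was used in 20" µl, and later "The volume of the mixture is adjusted to 25" µL. It names a Roche Transcriptor kit, then an MMLV mix from a kit described as both Invitrogen and Roche. The section on extraction of total RNA says 140 µL "of peripheral blood were used", whereas the Biochemical tests section describes two tubes with 100 µL each from a 4 mL draw.

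**The concern.** Each reported value is a ratio, target over β-actin. If β-actin expression changes more in one group than in another, all three ratios move by the same factor in the same direction. A relative rise in the berberine group produces the pattern that the hypothesis predicts: three inflammatory genes falling together. A reader would naturally take that agreement as mutual confirmation, when it could come from the common denominator alone.

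The quality checks in the plan address RNA purity, RNA integrity and assay precision. None of them asks whether the reference is stable. Specific objective 5, which compares obese subjects with controls, uses the same unchecked denominator.

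**Working it through.** **Plan's own figure.** The plan gives no effect size, SD or power to reproduce. The only figure bearing on the assay input is the 500 µg, checked in step 5.

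**1. Effect of a moving reference.** On the log2 scale, log2(ratio) = log2(target) − log2(β-actin). If the targets do not change and β-actin shifts by *s* cycles in Group 3 relative to its comparator, every ratio is multiplied by 2^(−*s*), taking 100% efficiency (assumed).

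| β-actin shift *s* (cycles) | Factor on all three ratios | Apparent change |
|---|---|---|
| +0.25 | 2^(−0.25) = 0.841 | −16% |
| +0.5 | 2^(−0.5) = 0.707 | −29% |
| +1 | 2^(−1) = 0.500 | −50% |
| −0.5 | 2^(0.5) = 1.414 | +41% |

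The last row also shows masking: a true 29% fall combined with a 0.5-cycle fall in β-actin gives 0.707 × 1.414 = 1.00, so no change is seen. A shift that is equal in all groups cancels between groups but not in a before-after comparison.

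**2. Chance of a false finding in one gene.** Assumptions: 30 per group (90 obese patients split equally), analysis on the log2 scale, two-sided 0.05, no true effect, and a β-actin rise of 0.5 cycle. The probability that a given gene is significant is 73%, 49% or 25% when the SD of the normalised readout is 0.75, 1.0 or 1.5.

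**3. Chance that all three fall together.** A simulation used a shared reference, no true effect, 6,000 runs per setting, target SD 0.7 to 1.2 and reference SD 0.3 to 0.9 (all assumed). All three genes were significantly lower in about 0.2% of trials or fewer with no shift, in 5% to 39% with a 0.5-cycle rise, and in 47% to 99.7% with a 1-cycle rise.

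**4. Does the input amount matter to the ratio?** If the input is wrong by a factor *f* for both target and reference, then (*f* × target)/(*f* × β-actin) = target/β-actin. For example, (1000 × 8)/(1000 × 100) = 8/100 = 0.08. A common input error cancels, provided reverse transcription is linear.

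**5. The 500 µg figure.**
- From 140 µL of blood: 500/0.140 = 3,571 µg/mL = 3.57 mg/mL.
- From 2 × 100 µL: 500/0.200 = 2,500 µg/mL.
- From the entire 4 mL draw: 500/4 = 125 µg/mL.
- Concentration: 500/20 = 25 µg/µL. In the 25 µL mix, reagents other than water and enzyme take 2.5 + 0.5 + 2.5 + 1 = 6.5 µL, leaving at most 18.5 µL for sample, so at least 500/18.5 = 27 µg/µL.
- The documents give no RNA yield. Assuming 1 to 20 µg per mL of blood, 140 µL supplies 0.14 to 2.8 µg, so 500 µg is about 3,600 to 180 times too much. At an assumed 50 µg/mL it is still 71 times too much.
- Read as 500 ng, the requirement is 0.5/0.140 = 3.57 µg/mL, inside the assumed range. A unit slip is the simplest explanation.

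**The case against.** The strongest reply is that nothing in the documents shows β-actin moving. The section on berberine and inflammation says "it inhibits the activation of SRC and cell mobility by TLR in macrophages", but it refers to macrophages stimulated with LPS. It says nothing about β-actin mRNA in patients' blood or about the direction of any change. Groups 2 and 3 both receive the nutritional plan and exercise, so effects of weight loss and training on β-actin should largely cancel in the contrast that isolates berberine. β-actin is also measured in the same assay and RNA is quantified, so the material for a check probably exists. All of this stands. It makes the point an unguarded risk whose missing element is an instruction to look.

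A reader might also infer that the implausible 500 µg causes or worsens the artefact. The documents do not support that: step 4 shows that a common input error drops out of the ratio. Nor do they state an impossible RNA input, because the 500 µg is described as cDNA and no RNA input mass is given anywhere.

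A pass/fail limit on the β-actin shift would also be hard to defend. With 30 per group the 95% half-width is about 2.00 × SD × √(2/30) = 0.52 × SD, that is 0.26, 0.39 or 0.52 cycle at an assumed SD of 0.5, 0.75 or 1. At an SD of 1 the interval could not exclude 0.5 cycle in both directions even with no true shift.

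**Conclusion.** The point holds as a limit on interpretation. Three readouts with one unvalidated denominator do not give three independent pieces of evidence. A relative β-actin rise of 0.25 to 1 cycle in Group 3 would lower all of them by 16% to 50%, and a fall would raise them or conceal a true effect. At the assumed sample size and SDs, a 0.5-cycle rise is enough to make false joint inhibition a realistic outcome (5% to 39%).

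This rests on assumed PCR efficiency, group size, SDs and shift sizes. It does not establish that any shift occurs or that a finding of inhibition would be false. The documents also never call these genes primary endpoints; they are the dependent variables of the general objective.

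The 500 µg figure and the conflicting volumes, kits and blood amounts are a separate reporting error, probably a unit slip in the first case. They need correction so that the assay can be understood and the RNA input is known.

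**What to change.** **Reference gene.**
1. From the β-actin and RNA concentration data, tabulate β-actin quantity per unit of RNA put into reverse transcription, by group and visit, with a confidence interval for the Group 3 minus Group 2 change.
2. As a sensitivity analysis, report NLRP3, IL-1β and TNF-α per unit of RNA input.
3. Attribute a fall to the targets only if both normalisations point the same way. Set no numerical trigger, since the documents give no SD to support one.

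**Cost.** One extra table and no new assay, provided the RNA mass or volume put into each reaction was recorded. If it was not, say so and limit the claim accordingly. Per-RNA values carry the added error of RNA quantification, so uncertainty is wider. An inhibition claim becomes harder to make if the reference gene moves. A second reference gene would also test stability, but that is new laboratory work.

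**Separate correction.** Replace the 500 µg with the RNA input mass actually used. Reconcile the 20 and 25 µL reaction volumes, the two kit descriptions, and the 140 µL and 2 × 100 µL blood volumes. The abstract speaks of patients already studied, so this should record what was done; repeating reverse transcription to standardise it would be new work.
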